- The patients will be randomized into the traditional vs. oral treatment groups (see below for details and protocol). The protocol for each group will be placed in sealed envelopes, 65 for each group, and picked randomly for each patient.
- The patients will attend their normal preoperative visits with the surgical team as well as their regularly scheduled preoperative clearance visit with the medical doctor (Surgery Welcome Center)
- Standard preoperative labs will be obtained (hematocrit, basic metabolic panel), at their preoperative appointment
- Additional preoperative labs will include urine specific gravity to monitor patient hydration which will be obtained the morning of surgery; this will be paid for by the CJR research fund.
- Standard laboratory values (hematocrit and basic metabolic panel) will be obtained postoperative day #1 and #2, if the patient has not been discharged.
- Urine output will be monitored on postoperative day #1 and #2 which is standard protocol
- Additional test will include urine specific gravity on postoperative day #1 and #2 as a marker of hydration as long as the patient is still in the hospital. If the patient is discharged postoperative day #1 we will collect this once in the morning, and once more before they are discharged. Payment of the cost of these laboratory evaluations will come from CJR research funds.
- Patients are encouraged to attend physical therapy 2-3 times a week for 6 weeks. Physical therapy log is attached with ROM and Girth measurement collected once a week for 4 weeks.
- Hematocrit, basic metabolic panel and urine specific gravity 2 weeks postoperatively at their routine follow-up visit will also be obtained. The cost of these laboratory tests will come from CJR research funding.
- Sixty-five patients in each group will be recruited for this study (see stats for power analysis). We will increase our number of enrollment to 75 in each group to account for patients that drop out and withdrawals from the study.

Traditional Fluid Protocol

- NPO Clears and Food after midnight.
- 2 Liters of lactated ringers administered by anesthesia intraoperatively.
- Postoperatively - 2 Liters of Crystalloid while in PACU and Inpatient Room for a Total of 4 Liters of Crystalloid within 24 hours.
 - Patient will receive 500 milliliters while in PACU and 1500 milliliters while in their Inpatient Room, for a total of 2 Liters.

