Based on my reading of the fluid management protocol, the study evaluates the hypothesis that the euvoolemia regimen leads to better outcomes than the traditional regimen. The former corresponds to the treatment group and the latter to the control group for the analysis, and assuming that the two groups demonstrate similarities in terms of potential pre-treatment confounding variables, such as measures obtained from preoperative history and physical, a comparison of post-treatment outcomes seems appropriate (e.g., t-tests). Even under random assignment to treatment, checks can be performed to ensure effective equivalence of confounders across treatment and control groups, an essential step in the case of small samples. If the results of such checks reveal potential confounding, including control variables in the analysis may be appropriate (e.g., in a linear regression) or a matching design to generate treatment-control pairs can be used.

While I do not have any substantive training in this field, it seems that some of the outcomes listed in the Procedures: Primary Outcomes section of the protocol may be mediated by others. For example, the association between receiving the treatment and readmission or length of hospitalization may be mediated by some of the other outcomes listed. Are there any known or suspected mediators at this point, either from the list of outcomes or beyond?

Concerning statistical power, in the figure below I calculate power (y-axis) for a range of hypothesised values of estimated effect sizes (colored lines), sample sizes per treatment and control group (x-axis), and arbitrarily chosen levels of significance (α) across the panels. Regarding α , I start with 0.05 and then make an adjustment based on an arbitrary number of hypotheses to be evaluated (eight, in this demonstration). The solid horizontal line at 0.8 represents the commonly accepted power value. As an example from Figure 1(b), for a medium-high effect size of 0.6 (green line) and evaluating eight hypotheses, in order to achieve power of 0.8 would require approximately 65 participants in each of the treatment and control groups.

[figure not shown]

Figure 1: Power calculations for hypothetical effect sizes and sample sizes (per group) at given values of α . The left panel uses $\alpha = 0.05$ and the right panel employs a Bonferroni correction for multiple hypotheses. In this case, evaluating eight hypotheses with a desired α of 0.05 yields an adjusted α of 0.00625.

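### The 80% power at 65 per group (d = 0.6, alpha 0.05/8 = 0.00625) holds only for one-sided t-tests; two-sided it is 73.8%, and the readable text does not say which is meant

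*Combined protocol and SAP*

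**What the plan says.** Section 9 (Methods of Evaluation) contains the only sample-size reasoning in the document. It suggests that "a comparison of post-treatment outcomes seems appropriate (e.g., t-tests") and then shows power curves under two significance levels, 0.05 and a Bonferroni-corrected level. According to the Figure 1 caption, "evaluating eight hypotheses with a desired α of 0.05 yields an adjusted α of 0.00625". Reading from panel (b), the text concludes for an effect size of 0.6 that "in order to achieve power of 0.8 would require approximately 65 participants in each of the treatment and control groups".

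The section presents this as an illustration. Its author says the calculation will "make an adjustment based on an arbitrary number of hypotheses to be evaluated (eight, in this demonstration"). Section 2 (Procedures) nevertheless takes the number as the trial's size: "Sixty-five patients in each group will be recruited for this study (see stats for power analysis"). It then adds: "We will increase our number of enrollment to 75 in each group to account for patients that drop out and withdrawals from the study". The same section describes the allocation material: "The protocol for each group will be placed in sealed envelopes, 65 for each group, and picked randomly for each patient". The Patient Withdrawal paragraph says that data from patients who withdraw are deleted and not analysed.

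On direction, section 9 states that "the study evaluates the hypothesis that the euvoolemia regimen leads to better outcomes than the traditional regimen". Section 6, on benefits, says it is not known whether the two protocols will differ. No readable passage calls any test one-sided or two-sided.

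**The concern.** A power figure for a t-test is incomplete without the sidedness. At a fixed per-test alpha, the two choices give different sample sizes. Here the difference is large enough to decide whether the adopted 65 per group meets the 80% target. A reader who assumes the usual two-sided t-test will take the 80% at face value, although under that assumption it is about 74%. The chance of missing a true effect of 0.6 is then about 26% rather than 20%.

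The extra ten patients per group do not settle the matter. They are there to replace dropouts and withdrawals, and withdrawn patients contribute no data. In addition, envelopes are described for only 65 per group, so it is unclear whether the extra ten would be randomised at all.

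**Working it through.** **Inputs.** From section 9: standardised difference d = 0.6; per-test alpha 0.05/8 = 0.00625; target power 0.80; two-sample t-test. From section 2: equal groups, 65 per group adopted, 75 per group to be enrolled. Sidedness is not given, so both versions were run.

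**Formula.** With n per group, the degrees of freedom are 2n − 2 and the noncentrality parameter is d × √(n/2). Power is the probability that a noncentral t variable exceeds the critical value. That value cuts off 0.00625 in one tail (one-sided) or 0.00625/2 = 0.003125 in each tail (two-sided).

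**At n = 65.** Degrees of freedom = 128; noncentrality = 0.6 × √32.5 = 3.42.
- One-sided: critical value 2.53, power 81.1%.
- Two-sided: critical value 2.78, power 73.8%.

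**Reproducing the plan's figure.**

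| Version, d = 0.6, alpha 0.00625 | n per group for 80% | Power at 65 |
|---|---|---|
| One-sided t | 63.5, so 64 | 81.1% |
| One-sided normal approximation | 61.95, so 62 | 82.2% |
| Two-sided t | 72.9, so 73 | 73.8% |
| Two-sided normal approximation | 71.04, so 72 | 75.4% |

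The normal approximation uses n = 2(z_alpha + z_power)²/d². Two-sided, this is 2 × (2.734 + 0.842)²/0.36 = 71.04. One-sided, it is 2 × (2.498 + 0.842)²/0.36 = 61.95 (worked with unrounded z values).

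The one-sided t-test reproduces an approximate 65: its requirement is one patient lower. The two-sided t-test needs 73 − 65 = 8 more per group, or 8/65 = 12%. The word *approximately* does not cover that gap, and neither does switching to a normal approximation.

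**Two-sided power across the possible analysed numbers.**

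| Analysed per group | 65 | 70 | 72 | 73 | 75 |
|---|---|---|---|---|---|
| Power | 73.8% | 77.8% | 79.3% | 80.05% | 81.4% |

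With equal losses, two-sided power stays at 80% only if at most 75 − 73 = 2 per group are lost, against an allowance of 75 − 65 = 10. If the whole allowance is used, power is back to 73.8%. With 65 analysed, the effect detectable with 80% power two-sided is d = 0.637, about 0.64. The one-sided test has 87.2% power at 75.

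**Envelopes.** Section 2 prepares 65 per group but enrols 75 per group, a gap of 10 in each arm. If only the 65 enveloped are randomised, every loss takes the analysed number below 65. If all 75 are randomised, 75 envelopes per group are needed.

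**The case against.** The strongest reply is that the plan's figure may be correct as it stands. The section 9 hypothesis is directional, and the one-sided t-test is the version that gives 65. The figure from which 65 was read is missing from this copy and may state the sidedness. All of this stands. A reader might infer that the plan's power calculation is wrong, or that the plan certainly omits the sidedness. The documents support neither, only that the readable text leaves the choice open.

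A second reply is that eight hypotheses is an admitted illustration, so precise power figures for it have limited meaning. That is also fair. A reader might infer that 65 per group cannot give 80% power two-sided at all; that is not so. At an unadjusted two-sided alpha of 0.05 the power at 65 is 92.4%, and with four Bonferroni-adjusted tests (0.05/4 = 0.0125) it is 81.1%. The shortfall belongs to the d = 0.6, eight-test case. But that is the case from which 65 was read, and section 2 cites the power analysis as the basis for the trial's size, so the stated 80% has to be judged there.

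A third reply is that the effect is modest: 81.4% if all 75 per group are analysed, and a shift in detectable effect from 0.60 to 0.64 if 65 are. This limits the importance of the point but does not remove it, because the extra ten are meant to be lost to dropout.

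Finally, a reader might infer that one-sided tests at 0.00625 would weaken error control. They would not in the stated direction: 8 × 0.00625 = 0.05. One-sided testing is a legitimate choice if it is declared with a direction for each outcome. Several listed outcomes, such as body weight, blood pressure and body temperature, have none stated.

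**Conclusion.** The point holds in conditional form. For the example that section 2 adopts (d = 0.6, alpha 0.00625, t-test, equal groups), 65 per group gives the stated 80% only if the tests are one-sided. Under two-sided testing, power is 73.8% with 65 analysed and 81.4% with 75, and 73 per group are needed. Confidence is high in the arithmetic and lower in the absence of a sidedness statement, because Figure 1 cannot be seen. The result assumes that the effect size is the mean difference divided by the standard deviation and that eight tests are made.

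Separately from sidedness, section 2 is inconsistent on its own figures: 65 envelopes per group do not serve 75 enrolled per group. It bears on this point because it decides whether the analysed number can exceed 65. The point should be fixed, but it does not call for a larger trial.

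**What to change.** In section 9, state whether the tests are one-sided or two-sided and make the power statement agree.

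- If two-sided, replace the claim with wording such as: *65 evaluable per group gives about 74% power for d = 0.6, or 80% for d = 0.64, at two-sided alpha 0.00625 in the illustrated case of eight hypotheses.*
- If one-sided, say so, give the direction of benefit for each tested outcome, and keep the 65.

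If Figure 1 already states the sidedness, repeat it in the text and check that 65 matches it.

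In section 2, reconcile the envelope count with enrolment: 75 envelopes per group if all 75 are to be randomised. If only 65 per group are randomised, say so and acknowledge that no allowance for dropout remains, since withdrawn patients' data are deleted.

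The cost is protocol wording and, if 75 are randomised, ten more envelopes per group. No patients are needed beyond the 75 per group already planned. The one downside, under two-sided testing, is a less favourable stated power.
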